3.3. Number of Patients and Sites

Up to 30 subjects in Cohort 1 and up to 40 subjects in Cohort 2 may be enrolled under this study at approximately ten (10) clinical sites.

3.4. Enrollment

All properly consented subjects will receive a unique, study subject identification (ID) number. Recruitment will occur at up to two (2) clinical sites in Cohort 1 and approximately ten (10) clinical sites in Cohort 2. Upon completion of screening, a subject is considered enrolled once an implant procedure is attempted. For Cohort 1, up to 30 subjects may be enrolled and implanted with up to ten (10) sentinel units. For Cohort 2, up to 40 subjects may be enrolled and implanted with up to 12 units total. Of the 12 units, no more than nine (9) will be dose-finding (VC-01-DF) and the remainder may be sentinel units.

Competitive enrollment of subjects is planned within each Cohort (e.g., subjects may be enrolled and implanted as frequently as possible by sites), but the Sponsor maintains the ability to alter the

pace of enrollment as necessary. Enrollment in Cohort 2 may advance prior to completion of Cohort 1. Any changes in the frequency and timing of enrollment will be communicated to sites by the Sponsor.

[figure not shown]
In both Cohorts, upon completion of Screening Visit 1 and after the Investigator has confirmed a subject has qualified for the study, sites must notify the Sponsor of the planned date of Visit 3 (Day 1– Implant Day). The Sponsor will confirm the acceptance of the planned implantation date in accordance with the Sponsor's manufacturing schedule for VC-01 units. Therefore, the rate of enrollment ultimately remains under the control of the Sponsor.

For Cohort 1 (Figure 1), the total duration of treatment (implantation of at least one unit) may be up to six (6) months for each subject, with the last sentinel unit explanted at Week 26 or earlier if requested by the Sponsor.

For Cohort 2 (Figure 2), the total duration of treatment (implantation of at least one unit) may be up to 12 months/Week 52 for each subject, with the last investigational unit(s) explanted at Week 52 or earlier if requested by the Sponsor.

[figure not shown]
Between Visit 3 (Day 1) and the final explant visit, investigational units may be explanted at varying time points as requested by the Sponsor.

Figure 1 - Cohort 1

▼ Denotes possible sentinel explant

Figure 2 – Cohort 2

▼ Denotes possible sentinel explant

4. STUDY POPULATION

This trial can fulfill its objectives only if appropriate subjects are enrolled. The following eligibility criteria are designed to select subjects for whom enrollment is considered appropriate. All relevant medical and non-medical conditions should be taken into consideration when deciding whether this protocol is suitable for a particular subject.

4.1. Entry Criteria

Subject eligibility should be reviewed and documented by an appropriately qualified member of the Investigator's trial team before subjects are enrolled in the trial. Subjects must meet all of the following inclusion criteria/exclusion criteria requirements at the time of the Screening Visit 1 (unless otherwise specified) to be eligible for enrollment into the trial. If screening laboratory test result(s) exclude a subject and the Investigator is reasonably certain that the results may be due to a lab error or may have been flawed for another reason, the lab test(s) may be repeated once during the Screening Period without prior permission from the Sponsor or its designee.

4.1.1. Inclusion Criteria

Cohort 1 and Cohort 2

- 1. Evidence of a personally signed and dated informed consent document (ICD) indicating that the subject has been informed of all aspects of the trial and agrees to participate in the trial
- 2. Men and non-pregnant women 18-65 years of age.
- 3. Diagnosis of T1DM for a minimum of three (3) years.
- 4. Stable, optimized diabetic regimen for at least 3 months.
- 5. Acceptable candidate for implantation and explantation procedures as assessed by Investigator
- 6. Willing and able to comply with scheduled visits, treatment plans, post-surgical care and restrictions, laboratory tests, and other study procedures.
- 7. All male subjects and female subjects of childbearing potential must practice highly-effective contraception, as described in Section 5.4.4, during the study and be willing and able to continue contraception until final explant.

Cohort 2 Only

- 8. Insulin dosage at screening <1 unit/kg/day (using previous seven days as average).
- 9. Willing to use a provided CGM System.
- 10. Willing and able to comply with daily entries on a study diary.

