6.2. Screening Visit 2 (Cohort 1: Week -1; Cohort 2: Week -4)

Subjects deemed to have met eligibility criteria after completion of Screening Visit 1 may return for Screening Visit 2. Visit 2 may be accelerated to occur sooner than indicated on Schedule of Assessments if results from Visit 1 have already been obtained and validate continued screening of the subject. Subjects must be fasted for this visit. The following procedures will be completed:

- Obtain weight and vitals.
- Review and confirm continued eligibility criteria.
- Obtain all laboratory samples per the Schedule of Assessments.

Note: The HLA-panel reactive antibody (PRA) and T1DM autoantibody samples may be collected at any time between Visit 1 and Visit 3, once the subject's study qualification is confirmed (Section 7.17.3).

- Cohort 2 Only:
 - Perform 4-hr MMTT. This is the baseline MMTT for efficacy evaluation.
 - Ultrasensitive C-peptide samples obtained in conjunction with 4-hr MMTT pre-stimulation (time = 0) and post-stimulation at the 90-minute (+/- 10 minutes) timepoint.
 - Dispense Continuous Glucose Monitor (CGM) equipment and provide instructions.
 Insert the first sensor at the clinic. Confirm the CGM is functioning prior to the subject leaving the clinic.
 - Dispense Self-Monitoring Blood Glucose (SMBG) equipment and provide instructions. Use of the meter provided by the Sponsor is required.
 - Dispense the study diary and provide instructions. This is where the subject will capture insulin doses, details on HEs, and SMBG values. Remind the subject that eligibility for the study requires daily compliance with entries between Visit 2 and Visit 3.
- Assess AEs and concomitant medications.
- Review Lifestyle Guidelines
 - Review dietary restrictions, physical activity, alcohol/tobacco/caffeine and other guidelines as described under Section 5.4.5.
 - Assess the subject's knowledge of the correct use of contraceptive method, confirm the current contraception method, and the subject's continued correct usage.

• Contact the Sponsor to report any schedule changes or updates to the implant date.

The expected duration of the Screening Period is approximately two (2) weeks total for Cohort 1 and approximately five (5) weeks total for Cohort 2.

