If the Enrollment Visit 3 (Day 1) is scheduled to occur beyond four (4) weeks (>28 days) for Cohort 1 or beyond six (6) weeks (>42 days) for Cohort 2 from the occurrence of Screening Visit 1, sites must contact the Sponsor before proceeding. Depending on the expected duration of the delay in conducting Visit 3, an Unscheduled Visit may be required to repeat certain screening procedures.

The overall Screening Period may be accelerated in Cohort 1 to less than two (2) weeks total if all visit procedures and results are completed and confirm the subject's eligibility for the trial. For Cohort 2, a minimum of two weeks must elapse between Visit 2 and Visit 3.

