7.12. Blood Glucose Monitoring – Cohort 2 Only

Throughout the trial in both Cohorts, the exogenous insulin requirements of enrolled subjects are managed and titrated by the Investigator (or qualified designee) as needed to maintain glycemic control in conjunction with standards of care. For purposes of this study, in Cohort 2, the diary entries made by the subjects (e.g., insulin doses, SMBG values, and HE occurrences) are the main sources of information available to the Investigator to assist with treatment decisions. CGM data may be utilized for treatment decisions in accordance with local labeling market approvals.

In addition to Investigator review of glucose trends, insulin dosing, and HE occurrences, the Sponsor will conduct routine reviews of blood glucose data. These data are collected as part of the required study procedures. Subjects record insulin dosing and all HE occurrences on a study diary and glucometer data are electronically downloaded. The data are then available in near real-time for review. If potentially concerning trends are evidenced for an

individual subject, the Sponsor will notify the Investigator and request for follow-up with the subject to occur if necessary.

Blood glucose monitoring is performed through various methods throughout Cohort 2 of this study to ensure proper glucose control:

- Laboratory tests (Section 7.17)
- Continuous Glucose Monitoring (Section 7.14)
- Self-Monitoring Blood Glucose (Section 7.15)

Data from these methods will be available to the Investigator via reports from laboratories, study diaries, and downloads or entries from CGM and SMBG meters to facilitate treatment decisions. The glucose monitoring data collected in Cohort 2 between Visit 2 (Week -4) and Visit 3 (Day 1) establishes the baseline profile of each subject's glycemic control (e.g., the percent time spent at various blood glucose cutoff points per CGM data, SMBG blood glucose levels, exogenous insulin doses, and frequency of HEs).

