7.14. Continuous Glucose Monitoring (CGM) – Cohort 2 Only

All subjects will be provided with a CGM system. Previous experience with CGM is not a requirement of study entry, but all subjects are required to use the Sponsor-provided CGM during study participation. Based on the labeled indication of the CGM in use, diabetes treatment decisions may be based on CGM data collected. Subjects relying on CGM data for treatment decisions will be required to be compliant with CGM usage and wear the CGM for the entire one-year study and also periodically sync the data, so that near-real time access may be available to the Investigator and Sponsor. A study reference manual will further outline the logistics with respect to CGM use and data collection.

All CGM supplies and instruction manuals will be provided by the Sponsor. Site personnel will instruct the subject on proper use and care at Visit 2 (Week -4) and as needed throughout the study. This training includes assisting the subject with the insertion of the first sensor needle prior to leaving the clinic at Visit 2. The CGM system is configured to alert the subject in the event blood glucose values approach hypoglycemic levels.

The CGM data collected for this trial will be used to evaluate secondary and exploratory endpoints. Data from the two weeks prior to appropriate clinic visits will be used in order to calculate the CGM endpoints (e.g., percent of time a subject's blood sugar is <54 mg/dL, $\ge54 \text{ to } <70 \text{ mg/dL}$, $\ge70 \text{ mg/dL}$ to $\le180 \text{ mg/dL}$, and >180 mg/dL). Other endpoints using CGM data may be evaluated and, if so, will be described in the Statistical Analysis Plan (SAP).

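### New CGM users may enter Cohort 2, and their glycaemic baseline falls within about their first 4-6 weeks on the study device, so the planned within-group changes cannot separate device learning from a graft effect.

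*Protocol*

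**What the plan says.** **Entry.** Inclusion 9 (Protocol 4.1.1) requires Cohort 2 subjects to be "Willing to use a provided CGM System". Protocol 7.14 is explicit: "Previous experience with CGM is not a requirement of study entry, but all subjects are required to use the Sponsor-provided CGM during study participation". Inclusion 4 requires "Stable, optimized diabetic regimen for at least 3 months" but does not mention CGM.

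**First use.** The Visit 2 list in Protocol 6.2 includes "Dispense Continuous Glucose Monitor (CGM) equipment and provide instructions", with the first sensor inserted in the clinic. The device is not masked: "The CGM system is configured to alert the subject in the event blood glucose values approach hypoglycemic levels". Protocol 7.12 and 7.14 allow CGM data to guide treatment decisions where labelling permits.

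**Baseline.** Protocol 6.2 sets the shortest interval before implant: "For Cohort 2, a minimum of two weeks must elapse between Visit 2 and Visit 3". Protocol 7.12 then says "The glucose monitoring data collected in Cohort 2 between Visit 2 (Week -4) and Visit 3 (Day 1) establishes the baseline profile", and that profile covers CGM ranges, SMBG, insulin doses and hypoglycaemic events (HEs). SAP 7.2.6.3.1 and 7.2.6.4 to 7.2.6.6 make this operational. They count back from Day -1 for up to 28 days, leave out SOGCT and MMTT days, and fill any shortfall with post-implant days from Day 4.

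**Analysis.** SAP 7.3.7.3 analyses change to Weeks 16, 20, 26, 39 and 52 in time in range, average daily insulin dose and HE frequency by ANCOVA, with treatment group (number of VC-01-DF units first implanted) and the relevant baseline as the only terms. It also summarises CGM percentages and their changes descriptively within each treatment group. The Visit 1 list in Protocol 6.1 does not name prior CGM use.

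**The concern.** A three-month stable regimen does not make the baseline stable if the study then changes the monitoring tool. A subject new to CGM receives live readings and low-glucose alerts at Visit 2. Measuring baseline on the device removes the immediate effect of wearing it. It does not remove further change as subject and investigator learn to act on the data, and that change would fall between baseline and Weeks 16-52. Protocol 7.12 encourages frequent contact for insulin adjustment over the same months.

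With no untreated arm, within-group change is what will be read as clinical benefit. Time in range, HEs and insulin dose are most of the clinical efficacy evidence beyond C-peptide, and Protocol 1.4.2.2 lists better glycaemic control, lower insulin dose and fewer HEs as possible benefits of VC-01. No planned output separates the two sources of improvement.

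**Working it through.** The plan states no figure on this point and Protocol 10.1 tests no hypothesis, so there is nothing to reproduce. Two checks apply.

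**1. Where the baseline falls in device time**

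Inputs: Visit 2 is device day 1 and an MMTT day, so it is left out. There is no Day 0. The window is Day -28 to Day -1, topped up from Day 4 to reach 28 days. Data are assumed complete.

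| Visit 2 on | Pre-implant days used | Top-up days | Last baseline day | Device day then |
|---|---|---|---|---|
| Day -14 (two-week minimum) | 13 | 15 (Days 4-18) | Day 18 | 14 + 18 = 32 |
| Day -21 | 20 | 8 (Days 4-11) | Day 11 | 21 + 11 = 32 |
| Day -28 | 27 | 1 (Day 4) | Day 4 | 28 + 4 = 32 |
| Day -29 | 28 | 0 | Day -1 | 29 |
| Day -35 | 28 | 0 | Day -1 | 35 |
| Day -41 | 28 | 0 | Day -1 | 41 |

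The baseline ends between device days 29 and 41, that is within about the first 4-6 weeks of wear. Missing days would push the end later when top-up applies. So would a screening period beyond 42 days, for which Protocol 6.2 requires sponsor contact.

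For comparison, the Week 16 CGM window is the 14 days before target Day 113, or Days 99-112. With Visit 2 on Day -14, those are device days 14 + 99 = 113 to 14 + 112 = 126. The earliest outcome is therefore read about four months into wear, and Week 52 about a year in.

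**2. Size of the shift under stated assumptions**

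The documents give neither the share of new users nor any gain after baseline. Assumed: share 20-60%, gain 2-6 percentage points of time in range.

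Shift in mean change = share × gain. One point of a day is 1440/100 = 14.4 minutes.

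- Low: 0.20 × 2 = 0.4 points, 5.8 min/day
- Middle: 0.40 × 4 = 1.6 points, 23 min/day
- High: 0.60 × 6 = 3.6 points, 52 min/day

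With no gain after baseline the shift is zero. For a contrast between two unit-number groups, the shift is (difference in new-user share) × gain, which is zero when the shares are equal. Protocol 3.2 lets the number of units vary between subjects and be chosen from accruing C-peptide results, so equal shares are not assured.

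**The case against.** **Baseline length.** From Protocol 7.12 and the two-week minimum, a reader might infer that a new user's baseline is only the first 2-4 weeks of wear. The SAP does not support that: its Day 4 rule fills short baselines to 28 days, so even a two-week Visit 2 to Visit 3 interval gives a baseline running to device day 32. This lengthens the baseline but leaves it early in device use.

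**No documented learning effect.** Nothing in the documents shows that glycaemia keeps improving after a month on CGM, and no direction is given for insulin dose or HEs. Protocol 7.12 names diary entries as the main source for treatment decisions. This stands. The size is unknown and could be zero.

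**Descriptive status.** Secondary p-values are descriptive. C-peptide is measured at the same visits, so readers can set glycaemic gains beside graft output. Fourteen consecutive zero-insulin days (SAP 7.2.6.3.2) could hardly come from learning to use a CGM. All of this limits the damage. But a descriptive label deals with multiplicity, not with bias in a mean change, and no planned table makes the comparison with C-peptide.

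**Other changes.** The study meter, daily diary and sponsor glucose review also begin around Visit 2 for everyone in Cohort 2, so splitting by prior CGM use would not isolate the device completely. That also stands.

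**Recording.** The CRF and study reference manual are not among the documents, so prior CGM use may already be captured. Protocol 6.1 does not list it, and no analysis uses it.

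**Conclusion.** The point holds for within-group change from baseline in the Cohort 2 time-in-range, HE and insulin-dose endpoints. It rests on documented facts: new users are eligible, the device is live and first supplied at Visit 2, the baseline ends by about device week 6, there is no untreated control, and no analysis term or table uses prior CGM use. The size rests wholly on assumption: 0.4-3.6 points of time in range for the ranges above, nothing if learning is complete by the end of baseline.

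Three stronger readings are not supported.

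- **That the trial's main result is at risk.** The primary endpoint and the other C-peptide endpoints do not depend on CGM skill.
- **That false positives can be quantified.** Assuming an SD of change of 8-12 points, a pooled 95% interval on 40 subjects would exclude zero with no graft effect in about 6% of trials at 0.4 points, 13-24% at 1.6 and 46-79% at 3.6. The SAP plans no pooled one-sample interval. In four equal groups of 10 (also assumed) the figures fall to about 5%, 7-9% and 14-25%. All are illustrative only.
- **That a covariate would cure it.** A prior-CGM term adjusts contrasts between groups. Each group's adjusted mean still averages over new and prior users, so the shift remains.

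**What to change.** 1. Record prior CGM use at Visit 1 as none, under 3 months, or 3 months or more.
2. In SAP 7.3.7.3, report the CGM, HE and insulin-dose changes from baseline separately for prior and new CGM users. A prior-CGM covariate is optional, and only as an aid to contrasts between unit-number groups.
3. Tabulate the same changes by C-peptide status at that visit. MMTTs are already scheduled at Weeks 16, 20, 26, 39 and 52. Define the negative-control group as subjects whose MMTT C-peptide values are all ≤0.1 ng/mL, the level SAP 7.2.6.1 already sets to zero, or who are undetectable on the ultrasensitive sample already drawn. The 0.2 ng/mL response threshold is not suitable: values between 0.1 and 0.2 count in the AUC and may reflect graft output.

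The cost is one CRF item and a few tables, with no change to eligibility, visits or treatment. The subgroups will be small. Grouping by C-peptide status uses post-baseline information, so that table can only be descriptive. Prior use is best captured at screening, since later recall is weaker.

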4.1.2. Exclusion Criteria

Cohort 1 and Cohort 2

1. Current use of any oral diabetes-specific medication.

- 2. Medical history of islet cell, kidney, and/or pancreas transplant.
- 3. Occurrence of two (2) or more severe, unexplained hypoglycemic events within six (6) months of enrollment
- 4. Known causes of diabetes other than T1DM.
- 5. Diabetic complications such as:
 - a. Renal dysfunction [macroalbuminuria defined as protein of 2+ or greater on dipstick, MDRD eGFR <60 mL/min/1.73m2]
 - b. Proliferative retinopathy (active or untreated)
 - c. Diabetic foot ulcers
 - d. Amputations attributable to diabetes
 - e. Severe peripheral neuropathy
- 6. Hemoglobin A1C (HbA1C) level of >10.0%.
- 7. Non-compliance with current anti-diabetic regimen.
- 8. Significant skin conditions in area(s) targeted for implantation. Examples include but are not limited to recurrent boils/furuncles, extensive surgery or scarring, or lipodystrophy.
- 9. Uncontrolled or untreated thyroid disease or adrenal insufficiency.
- 10. Current alcohol and/or drug (including marijuana) abuse or history of abuse within five (5) years of enrollment.
- 11. Positive urine drug screen for illicit substances of abuse at screening (Cohort 1) or screening and enrollment (Cohort 2). Note: A positive urine drug screen for marijuana does not automatically exclude a patient. If positive, the Investigator must determine if the extent of the subject's marijuana use meets the clinical definition of abuse.
- 12. Prior history of malignancy, except for:
 - a. Basal cell carcinoma of the skin;
 - b. Squamous cell carcinoma of the skin that has been recurrence free for ≥ five (5) years;
 - c. Appropriately treated in situ carcinoma of the cervix.
- 13. Known allergies to portions of the cellular excipients used as cell preservation solution or the PEC-01 manufacturing process (i.e., bovine, porcine allergies).
- 14. History of severe asthma or chronic obstructive pulmonary disease (COPD).
- 15. Body mass index (BMI) ≥32 kg/m2 or <18 kg/m2 at screening
- 16. Active hepatobiliary disease or an AST or ALT >1.5 x ULN at screening or a total bilirubin >1.5 x ULN unless the subject has a history of Gilbert's disease.
- 17. Active infection or known history of Hepatitis B or C.
- 18. Positive serology for human immunodeficiency virus (HIV) at screening.
- 19. Evidence of tuberculosis (TB) infection.

- 20. Other abnormal labs at screening:
 - a. Platelets <100,000.
 - b. Hgb <12 g/dL (males) or <11 g/dL (females).
 - c. Fasting triglycerides >500 mg/dL.
 - d. Estimated Glomerular Filtration Rate (eGFR) <60 mL/min/1.73 m2
 - e. Clinical lab value outside normal range, unless deemed as not clinically significant by the Investigator. Determination of clinical significance of a clinical lab value outside of normal range may also be evaluated by the Sponsor on a case-by-case basis.
- 21. Sustained hypertension defined as average systolic ≥160 mmHg or diastolic ≥90 mmHg at screening.
- 22. 12-lead electrocardiogram (ECG) findings demonstrating:
 - a. QT interval (QTc) >450 msec for males or >470 msec for females at screening.
 - b. Any other abnormality deemed clinically significant requiring further clinical evaluation by the Investigator.
- 23. History of unstable angina or Class 3 or 4 congestive heart failure (CHF), or any of the following conditions or procedures within the past year: stroke, myocardial infarction, life-threatening arrhythmia, major cardiovascular procedure (e.g., angioplasty, planned angioplasty, or carotid endarterectomy), or any other clinically-significant cardiovascular diagnosis or procedure.
- 24. History of coagulopathy.
- 25. Immunosuppressant therapy in the previous 30 days and/or requirements for chronic immunosuppressive therapy during the study as these may influence the expected action of the cells or graft. Individuals currently on immunosuppressant therapy may be considered on a case-by-case basis after consultation with the Sponsor.
- 26. Prescribed corticosteroid therapy above physiologic replacement doses in the previous 30 days.
- 27. Participation in a study of an investigational drug, device, or graft within five half-lives of the experimental agent or 30 days prior to enrollment in this study, whichever is longer.
- 28. Planned surgery in the general location of the implanted units at any time during study participation.
- 29. In the opinion of the Investigator, the subject is not suitable for the trial. This includes clinically significant medical and non-medical conditions, and/or clinically-significant psychiatric disorders.

Cohort 2 Only

30. A detectable stimulated serum C-peptide at any time point during the Screening Period, defined as >0.2 ng/mL (>0.0667 nmol/L).

